Study Design	
 This is a randomized, open-label (sponsor blind), active-controlled, parallel-group, multi-center, event-driven study in non-dialysis subjects with anemia associated with chronic kidney disease (CKD). This study will comprise 4 study periods: a 4-week screening period, a 4-week placebo run-in period, a treatment period, and a follow-up period. Prior erythropoiesis-stimulating agent (ESA) therapy, if present, continues during the screening and run-in periods. ESAs refer to any rhEPO or methoxy PEG-epoetin beta. The total duration of the study is dependent upon the accumulation of at least 664 adjudicated first MACE (i.e., it is event-driven) unless review of interim data by the Independent Data Monitoring Committee (IDMC) recommends bringing the study to an earlier close. Subjects will be stratified by region, by whether they are currently using an ESA and by participation in the ambulatory blood pressure monitoring (ABPM) sub-study. Region and ESA use at study entry are considered to be stratification factors that are potentially prognostically important, i.e., predictive of study endpoints while participation in the ABPM sub-study is an administrative stratification factor intended solely to ensure a similar number of sub-study subjects in each of the two randomized groups. Following stratification, subjects will be randomized 1:1 to receive oral daprodustat or subcutaneous (SC) darbepoetin alfa.

Overview	Key Elements of the RAP
	
 Both treatment arms (daprodustat and darbepoetin alfa) will follow a protocol-specified randomized treatment dose adjustment algorithm to achieve and/or maintain Hgb within the target range of 10-11 g/dL inclusive. Dose changes will be made programmatically by the Interactive Response Technology (IRT) system for both randomized treatment arms.

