Prior ESA Type and Standardized Prior ESA Dose (U/week) at Randomization

 • During the screening period, subjects may be receiving ESAs in multiple ways, including: epoetin IV or SC, darbepoetin IV or SC, or methoxy PEG-epoetin beta IV or SC.

Demographic & Baseline Characteristics

- A subject’s prior ESA type will be determined from the records that contribute to the subject’s standardized prior ESA dose. The following categories of prior ESA type will be summarized:
 - Darbepoetin alfa only
 - Epoetin only
 - This group contains subjects using any of the following types of epoetin: epoetin alfa, epoetin beta, epoetin lambda, epoetin theta, and epoetin zeta.
 - Methoxy PEG-epoetin beta only
 - This group contains subjects using methoxy PEG-epoetin beta and pegzerepoetin alfa.
 - Multiple
 - This group contains subjects using any combination of the ESA types.
 - Missing

- The dose of ESA will be standardized to obtain a continuous single unit prior ESA dose in terms of epoetin IV U/week for the period from the Week -8 visit to the day before the Randomization date.

- All prior ESA therapy concomitant medication records from screening/run-in will be selected and ordered by start date and end date.

- The standardization will be carried with the following formula:
- For subjects taking epoetin IV:
 - Standardized ESA dose (U/week) = epoetin IV dose (U)*frequency
- For subjects taking epoetin SC:
 - Standardized ESA dose (U/week) = (161/113)*epoetin SC dose(units)*frequency
- For subjects taking darbepoetin IV or SC:
 - Standardized ESA dose (U/week) = 250*darbepoetin dose (µg)*frequency
- For subjects taking methoxy PEG-epoetin beta:
 - Standardized ESA dose (U/week) = 208*methoxy PEG-epoetin beta dose (µg)*frequency

Note: Frequency and Gap Factors defined as follows:

Frequency (from eCRF)	Frequency (for standardization formula)	Gap Factor
One time dose	see below	n/a
Four times per week	4	0.75 day
Three times per week	3	1.33 days
Two times per week	2	2.5 days
Every week	1	6 days
Every 10 days	0.70	9 days
Every 2 weeks	0.50	13 days

Demographic & Baseline Characteristics			
Every 3 weeks	0.33	20 days	
Every 4 weeks	0.25	27 days	
Every 5 weeks	0.20	34 days	
Every 6 weeks	0.167	41 days	
Every 8 weeks	0.125	55 days	

- If the frequency of the record is not 'one time dose', then duration is calculated as follows:
 - If the concomitant medication record start date \geq Randomization date, the duration of the record is 0.

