 - If the concomitant medication record end date + gap factor < Week -8 visit date, the duration of the record is 0.
 - If the concomitant medication record end date + gap factor \geq Week -8 visit date, the duration of a record will be calculated as Stop Date – Start Date +1 day, where:
 - Start date will be the latest of (concomitant medication record start date and the Week -8 visit date).
 - Stop date will be the concomitant medication record end date + gap factor.
- If the frequency of the record is 'one time dose', then:
 - If the concomitant medication record start date \geq Randomization date, the duration of the record is 0.
 - If Week -8 visit date \leq concomitant medication record start date, then:
 - Frequency (for standardization formula) = 1
 - Duration = 7 days
 - If concomitant medication record start date < Week -8 visit date, then:
 - Frequency (for standardization formula): $7 / [\text{earliest of (the day before the next sequential prior ESA concomitant medication record start date and the day before randomization)} - \text{start date of record} + 1 \text{ day}]$
 - If the earliest non-missing date of (the day before the next sequential prior ESA concomitant medication record start date and the day before randomization) < Week -8 visit date, the duration of the record is 0.
 - If the earliest non-missing date of (the day before the next sequential prior ESA concomitant medication record start date and the day before randomization) \geq Week -8 visit date, the duration of the record is calculated as Stop Date – Start Date + 1, where:
 - Start date will be the Week -8 visit date.
 - Stop date will be the earliest of (the day before the next sequential prior ESA concomitant medication record start date and the day before randomization)
- The total dose for each prior ESA record will be: Standardized dose*duration/7days
- A weighted mean will then be used to obtain the prior ESA dose:
 Mean prior ESA dose = $[(\text{ESA total dose}_{\text{Record 1}}) + \dots + (\text{ESA total dose}_{\text{Record n}})] / [(\text{Randomization Date} - \text{Week -8 Visit Date}) / 7 \text{ days}]$

Demographic & Baseline Characteristics
Baseline Body Mass Index (BMI)

 Calculated as baseline weight (kg) / [height (m)]²
Dosing Algorithm at Randomization

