Category	Covariates and / or Subgroups	Summary of Demographics & Baseline Characteristics Note: Include 'Missing' categories, if applicable.	Subgroup Analysis for Co-primary MACE & Principal Secondary Safety Endpoints Note: Do not include 'Missing' categories.	Subgroup Analysis for Co-primary Hgb Endpoints Note: Do not include 'Missing' categories.
	Black or African American Native Hawaiian or Other Pacific Islander White – Arabic/North African Heritage White – White/Caucasian/European Heritage Mixed Asian Race Mixed White Race Mixed Race			
Region	See Region categories defined in Section 10.9.1	Yes	Yes	Yes
Regions combined	USA, Non-USA	Yes	Yes	Yes
Country	See Countries listed in Section 10.9.1	Yes	No	No
Current ESA use at randomization	ESA non-user, ESA user, Missing	Yes	Yes	Yes
Prior ESA type at randomization	Darbepoetin alfa only, Epoetin only, Methoxy PEG-epoetin beta only, Multiple, Missing	Yes	No	No
Standardized prior ESA dose (U/week) ¹	Summary statistics of continuous values	Yes	No	No
Standardized prior ESA dose group ¹	< 3,000 U/week, ≥3,000 U/week, Missing	Yes	Yes	Yes
Baseline Hgb (g/dL)	Continuous covariate for Hgb co-primary	Yes	No	No

CONFIDENTIAL

200808

Category	Covariates and / or Subgroups	Summary of Demographics & Baseline Characteristics Note: Include 'Missing' categories, if applicable.	Subgroup Analysis for Co-primary MACE & Principal Secondary Safety Endpoints Note: Do not include 'Missing' categories.	Subgroup Analysis for Co-primary Hgb Endpoints Note: Do not include 'Missing' categories.
	analysis; summary statistics of continuous values			
Baseline Hgb group	< 9 g/dL, 9 - <10 g/dL, 10 - 11 g/dL, >11 g/dL, Missing	Yes	Yes	Yes
Baseline body mass index (kg/m ²)	Summary statistics of continuous values	Yes	No	No
Baseline body mass index group	<30 kg/m ² , ≥30 kg/m ² , Missing	Yes	Yes	Yes
Baseline weight (kg)	Summary statistics of continuous values	Yes	No	No
Baseline weight group	<75 kg, ≥75 kg, Missing	Yes	No	No
Baseline weight quartiles	Overall ITT Population Quartile 1: < xx kg Overall ITT Population Quartile 2: xx kg - < xx kg Overall ITT Population Quartile 3: xx kg - < xx kg Overall ITT Population Quartile 4: ≥ xx kg Missing	Yes	Yes	Yes
Baseline eGFR (mL/min/1.73m ²)	Summary statistics of continuous values	Yes	No	No
Baseline CKD stage (based on eGFR)	Stage 2: 60-89 mL/min/1.73m ² ; Stage 3: 30-<60 mL/min/1.73m ² ; Stage 4: 15 - <30 mL/min/1.73m ² ;	Yes	No	No

CONFIDENTIAL

200808

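### The standardized prior ESA dose lets a recurring record run past randomization, so records that began before Week -8 and end near randomization are overstated, and some subjects can cross the 3,000 U/week subgroup cut

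*SAP*

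**What the plan says.** The synopsis (SAP Section 1) describes "a 4-week screening period, a 4-week placebo run-in period, a treatment period, and a follow-up period", so Week -8 to randomization is nominally 56 days. Prior ESA therapy "continues during the screening and run-in periods".

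Section 10.6.2.2 standardizes the prior dose "for the period from the Week -8 visit to the day before the Randomization date". Each record's weekly dose is multiplied by a duration, and the sum is divided by the number of weeks between the Week -8 visit and randomization. For recurring-dose records:

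- left end: "Start date will be the latest of (concomitant medication record start date and the Week -8 visit date");
- right end: "Stop date will be the concomitant medication record end date + gap factor".

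The gap factors include 6 days (weekly), 13 (2-weekly), 27 (4-weekly) and 55 (8-weekly).

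One-time doses have two branches. If given before Week -8, "Stop date will be the earliest of (the day before the next sequential prior ESA concomitant medication record start date and the day before randomization"). If given inside the window, they get frequency 1 and a fixed 7 days.

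In Section 10.10.1 the "Standardized prior ESA dose group", split at 3,000 U/week, is a subgroup for MACE, the principal secondary endpoints and the Hgb co-primary. The continuous dose appears in the baseline table, overall and by hsCRP quartile.

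**The concern.** Numerator and denominator cover different periods. The left edge of a recurring record is trimmed to the window and the right edge is not, so the numerator can include days after randomization that the denominator excludes. A record's gap can also run over the start of the record that follows it, so the same days are counted twice.

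The omission does not look deliberate. The rule for one-time doses given before Week -8 limits the stop date at both the next record and randomization. Iron use by quarter (Section 10.6.3.2), which also uses gap factors, ends at the earliest of several dates including the quarter end.

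The excess from running past randomization is always upward and grows with the dosing interval. The 3,000 U/week split may therefore partly separate subjects by dosing schedule rather than by dose.

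**Working it through.** The SAP states no numerical result for this derivation, so the rule itself is applied.

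**Inputs.** Week -8 = day 0 and randomization = day 56 (4 + 4 weeks, nominal). Gap factors and frequencies come from Section 10.6.2.2, the 3,000 U/week cut from Section 10.10.1. Assumption: one record begun before day 0 and ending on day 55, the day before randomization.

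**Formula.** Duration = (end + gap) − 0 + 1. Ratio to the prescribed weekly dose = duration / 56. Lowest true dose that reaches the cut = 3,000 / ratio.

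| Frequency | Gap (days) | Duration (days) | Ratio | Lowest true dose placed in ≥3,000 |
|---|---|---|---|---|
| Weekly | 6 | 62 | 1.107 | about 2,710 |
| 2-weekly | 13 | 69 | 1.232 | about 2,435 |
| 4-weekly | 27 | 83 | 1.482 | about 2,024 |
| 8-weekly | 55 | 111 | 1.982 | about 1,514 |

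If the stop is limited to day 55, the duration is 56 days and the ratio is 1.000 in every row.

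**Window length.** For 4-weekly dosing the ratio is 76/49 = 1.551 with a 49-day window and 90/63 = 1.429 with a 63-day window. These lengths are assumed, to allow for visit timing.

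**Worked subject.** Darbepoetin 40 µg every 4 weeks, injected on days −1, 27 and 55.

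- Weekly dose: 250 × 40 × 0.25 = 2,500 U/week.
- SAP rule: 2,500 × 83/7 = 29,643 U; divided by 8 weeks = 3,705 U/week (≥3,000 group).
- Doses actually given in the window: 2 × 40 × 250 = 20,000 U; divided by 8 = 2,500 U/week (<3,000 group).

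The rule credits the remaining cover of the injection on day −1 and also the whole post-randomization cover of the one on day 55.

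**Overlap with the next record.** Two abutting 4-weekly records, days 0–27 and 28–55, have durations 27 + 27 − 0 + 1 = 55 and 55 + 27 − 28 + 1 = 55. The ratio is 110/56 = 1.96. Limiting only at randomization leaves (55 + 28)/56 = 1.48. Limiting the first record at its successor as well gives (28 + 28)/56 = 1.00.

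**Where there is no error.**

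- Same 4-weekly record, last injection on day 28 and no later record: 28 + 27 = day 55, duration 56, ratio 1.000.
- If the record end is the last injection, and that day is spread evenly over the 28 days before randomization (an assumption), the excess runs from 0 to 48.2% with mean 13.5/56 = 24.1%.
- Record that starts inside the window, with injections on days 14 and 42: duration 42 + 27 − 14 + 1 = 56, total 2,500 × 56/7 = 20,000 U, which is exactly the two doses given.

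**The case against.** The best defence is that the gap factor is not simply an overrun. For most rows it is the dosing interval less one day. A record that starts in the window and ends at its last injection therefore totals the doses given, all before randomization. In-window one-time doses are likewise credited in full with no limit. This stands. The defect lies in records that straddle Week -8 and in records whose gap overlaps a successor.

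The size also depends on how sites enter the end date, which the SAP does not define. Section 10.4.1.5 assumes a medication was taken on its reported stop date, which leans towards the last injection. A reader might infer that every user of a long-interval ESA carries the maximum excess. That would require every record end to be entered at about the day before randomization, and nothing in the SAP says so.

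A simple three-way minimum for the stop date would also be unsafe. Take a 4-weekly record ending 10 days before Week -8, with the next record starting 5 days before it. End plus gap is day 17, so the record passes the existing inclusion test, but the stop becomes day −6 and the duration −6 − 0 + 1 = −5 days. Two concurrent ESA records with the same start date would lose one dose. Both points stand and shape the fix.

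Finally, the variable is peripheral. The co-primary models adjust for current ESA use as randomized, the dose rule is the same in both arms, and subgroup results are read for consistency without multiplicity adjustment.

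**Conclusion.** The rule is wrong as written: against the SAP's own stated period and denominator, it overstates the dose for recurring records that began before Week -8 and end near randomization. With a 56-day window and a record end on the day before randomization, the excess is 11%, 23%, 48% and 98% for weekly, 2-weekly, 4-weekly and 8-weekly dosing. It is larger where a record's gap overlaps the next record.

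Three stronger readings are not supported:

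- That 48% is the ceiling. It is the 4-weekly figure only.
- That subjects are generally misclassified. Through the overrun at randomization, only those with a true dose in a band below 3,000 U/week (about 2,024–2,999 for 4-weekly) can move, and only upward. The SAP gives neither the frequency mix nor the dose distribution, so their number is unknown.
- That a co-primary result is biased. What changes is a baseline summary and one prespecified subgroup split.

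The figures rest on the nominal window and the assumed end date.

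**What to change.** In the recurring-dose rule of Section 10.6.2.2, define the stop date as the earliest of:

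1. record end plus gap factor;
2. the day before randomization;
3. where the next ESA record replaces this one rather than running alongside it, the day before that record starts.

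Add two provisions. If the resulting stop date is earlier than the start date used, the duration is 0. For concurrent ESA records only limits 1 and 2 apply, so that no dose is dropped.

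One consequence should be accepted knowingly: a recurring dose given shortly before randomization will count only for its days inside the window. A 4-weekly dose first given 6 days before randomization counts as 6/28 of a dose, while the same injection entered as a one-time dose counts in full. That follows the stated period.

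The cost is a few lines of SAP text and derivation code, including a way to tell replacement from concurrent records. No new data are needed.

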10.6.2.3. Randomized Treatment Discontinuation, Study Withdrawal and Possible Follow-up Time

Randomized Treatment Discontinuation, Study Withdrawal, and Possible Follow-up Time
Randomized Treatment Discontinuation

 ● $\text{Randomized Treatment Discontinuation Censored Time (days)} = \text{Treatment stop date} - \text{Treatment start date} + 1$ If the treatment stop date = death date for a subject, the subject will be censored and will not be counted as an event for treatment discontinuation summaries that exclude subjects who die while on treatment. ● $\text{Time to Randomized Treatment Discontinuation (days)} = \text{Treatment stop date} - \text{Treatment start date} + 1$ ● $\text{Randomized Treatment Person Years} = (\text{Cumulative total of time to randomized treatment discontinuation for subjects who discontinued randomized treatment} + \text{Cumulative total of randomized treatment discontinuation censoring time for subjects who did not discontinue randomized treatment}) / 365.25$ ● $\text{Randomized Treatment Discontinuation Incidence Rate (per 100 person years)} = 100 * \text{Number of subjects who discontinued randomized treatment} / \text{randomized treatment person years}$
Study Withdrawal

 ● $\text{Study Censored Time (days)} = \text{Study completion date} - \text{Randomization date} + 1$ ● $\text{Time to Study Withdrawal (days)} = \text{Study withdrawal date} - \text{Randomization date} + 1$ ● $\text{Study Person Years} = (\text{Cumulative total time to study withdrawal for subjects withdrawing from the study} + \text{Cumulative total of study censoring time for subjects who did not withdraw from study}) / 365.25$ ● $\text{Study Withdrawal Incidence Rate (per 100 person years)} = (100 * \text{Number of subjects who have withdrawn from study}) / \text{Study Person Years}$

Randomized Treatment Discontinuation, Study Withdrawal, and Possible Follow-up Time
Possible Follow-up Time

 • Possible follow-up time (days) = Study completion date or date of the middle of the end of study window for subjects who did not complete the study – randomization date + 1 • Total possible follow-up time (person years) = Cumulative total of possible follow-up time (days) for all subjects / 365.25

10.6.2.4. Prior and Concomitant Medications

Prior and Concomitant Medications
Non-randomized ESA use during treatment period

 • Subjects will be considered to have non-randomized ESA use during the treatment period if they have any ESA concomitant medication records with one of the following two reasons for medication: 
 ○ Non-randomized ESA treatment in addition to randomized treatment ○ Non-randomized ESA treatment instead of randomized treatment
Duration of non-randomized ESA use during treatment period

 • If there is only one concomitant medication record of non-randomized ESA use during the treatment period, then: 
 ○ Duration (days) = earliest of (concomitant medication record end date, last non-zero dose date + 1 day) – latest of (concomitant medication start date, treatment start date) + 1 day • If there are multiple concomitant medication records of non-randomized ESA use during the treatment period, then the duration of non-randomized ESA use will add the durations for all records, subtracting any overlapping days that may exist between the multiple records.
Clopidogrel start date for new clopidogrel users

 • New clopidogrel users are subjects who did not use clopidogrel on randomization day, but started their clopidogrel use after randomization during the on-treatment state for concomitant medications. To determine the start date of clopidogrel for the new users, only the first clopidogrel record during the on-treatment state for concomitant medications will be considered. The start date will be the first day subjects on both clopidogrel and randomized treatment.

10.6.2.5. Exposure and Compliance

Exposure and Compliance
Exposure

 • Exposure (days) = Treatment stop date – treatment start date + 1 day
Compliance

 • Compliance will be calculated based on data recorded in the Study Treatment Details eCRF pages and will only be calculated for subjects with a non-missing treatment start date, and will not be calculated after a subject’s treatment stop date, or study conclusion date for subjects who have a non-missing treatment start date and a missing treatment stop date. • A compliance category will be assigned to each randomized treatment exposure record according to the following tables. Exposure records corresponding to periods of dose

Exposure and Compliance																																																																																			

hold/zero-dose as assigned by the IRT will be categorized in the compliant category and any gaps between exposure records will be categorized in the under compliant category.
 
 ○ Daprodustat Doses 
  
 Under Compliant	Compliant	Over Compliant	
   
 Compliance for the exposure record < 80%	Compliance for the exposure record ≥ 80% and ≤ 120%	Compliance for the exposure record > 120%	
 
 Where compliance for the exposure record is calculated as 100% * [# dispensed – (# returned + # lost)] / # tablets per day / (dose stop date – dose start date +1)	
 
 # tablets per day: 1 tablet per day: 1mg, 2mg, 4mg, 6mg, 8mg, 10mg 2 tablets per day: 12mg, 16mg 3 tablets per day: 24mg	
  
 ○ Darbe Every 4 Week Exposure Records: Based on Number of Doses Given 
  
 Duration of Exposure Record	Under Compliant	Compliant	Over Compliant	
   
 1 – 14 days	< 1 dose	1 dose	> 1 dose	
 
 15 – 42 days	< 1 dose	1 or 2 doses	> 2 doses	
 
 43 – 70 days	< 2 doses	2 or 3 doses	> 3 doses	
 
 71 – 98 days	< 3 doses	3 or 4 doses	> 4 doses	
 
 99 – 126 days	< 4 doses	4 or 5 doses	> 5 doses	
 
 Etc.				
  
 ○ Darbe Every 2 Week Exposure Records: Based on Number of Doses Given 
  
 Duration of Exposure Record	Under Compliant	Compliant	Over Compliant	
   
 1 – 7 days	< 1 dose	1 dose	> 1 dose	
 
 8 – 21 days	< 1 dose	1 or 2 doses	> 2 doses	
 
 22 – 35 days	< 2 doses	2 or 3 doses	> 3 doses	
 
 36 – 49 days	< 3 doses	3 or 4 doses	> 4 doses	
 
 50 – 63 days	< 4 doses	4 or 5 doses	> 5 doses	
 
 64 – 77 days	< 5 doses	5 or 6 doses	> 6 doses	
 
 78 – 91 days	< 6 doses	6 or 7 doses	> 7 doses	
 
 92 – 105 days	< 7 doses	7 or 8 doses	> 8 doses	
 
 Etc.				
  
 				Under Compliant	Compliant	Over Compliant	Compliance for the exposure record < 80%	Compliance for the exposure record ≥ 80% and ≤ 120%	Compliance for the exposure record > 120%	Where compliance for the exposure record is calculated as 100% * [# dispensed – (# returned + # lost)] / # tablets per day / (dose stop date – dose start date +1)			# tablets per day: 1 tablet per day: 1mg, 2mg, 4mg, 6mg, 8mg, 10mg 2 tablets per day: 12mg, 16mg 3 tablets per day: 24mg			Duration of Exposure Record	Under Compliant	Compliant	Over Compliant	1 – 14 days	< 1 dose	1 dose	> 1 dose	15 – 42 days	< 1 dose	1 or 2 doses	> 2 doses	43 – 70 days	< 2 doses	2 or 3 doses	> 3 doses	71 – 98 days	< 3 doses	3 or 4 doses	> 4 doses	99 – 126 days	< 4 doses	4 or 5 doses	> 5 doses	Etc.				Duration of Exposure Record	Under Compliant	Compliant	Over Compliant	1 – 7 days	< 1 dose	1 dose	> 1 dose	8 – 21 days	< 1 dose	1 or 2 doses	> 2 doses	22 – 35 days	< 2 doses	2 or 3 doses	> 3 doses	36 – 49 days	< 3 doses	3 or 4 doses	> 4 doses	50 – 63 days	< 4 doses	4 or 5 doses	> 5 doses	64 – 77 days	< 5 doses	5 or 6 doses	> 6 doses	78 – 91 days	< 6 doses	6 or 7 doses	> 7 doses	92 – 105 days	< 7 doses	7 or 8 doses	> 8 doses	Etc.			
Under Compliant	Compliant	Over Compliant																																																																																	
Compliance for the exposure record < 80%	Compliance for the exposure record ≥ 80% and ≤ 120%	Compliance for the exposure record > 120%																																																																																	
Where compliance for the exposure record is calculated as 100% * [# dispensed – (# returned + # lost)] / # tablets per day / (dose stop date – dose start date +1)																																																																																			

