10.1. Appendix 1: Protocol Deviation Management and Definitions for Per-Protocol Population

10.1.1. Exclusions from Per-Protocol Population

Exclusions from the PP population include events that, if they should occur, might:

- Directly impact the hemoglobin efficacy endpoint; or
- Lead to permanent discontinuation of study treatment or study withdrawal and hence indirectly impact the efficacy endpoint by causing data to be missing.

The following criteria define the events which, if they occur prior to the end of the EP, may lead to exclusion of a subject from the PP population. Exclusions from the PP Population will be subject to blinded review by the study team. The study team will also review the listing of unique concomitant medication terms to identify the prohibited medications. These reviews will occur before database has been unblinded for analysis.

A subject meeting any of the following criteria may be excluded from the Per-Protocol population:

Number	Exclusion Description
01	Baseline HemoCue Hgb value outside of Randomization (Day 1) Hgb entry criteria range
02	Less than 5 out of 7 scheduled evaluable ¹ Hgb values ² from the EP
03	Non-compliance with randomized treatment (compliance category of under compliant or over compliant) during the EP, based on eCRF randomized medication exposure and compliance forms
04	Inadequate iron status during EP, defined as ferritin \leq 100 ng/mL on two consecutive scheduled visits or TSAT \leq 20% on two consecutive scheduled visits
05	Subject received prohibited medication ³ for more than two weeks during EP

NOTES:

1. See Section 10.6.3.
2. Based on central laboratory Hgb values. If central laboratory Hgb value is missing, a non-missing HemoCue Hgb value will be used.
3. Prohibited medications include strong inhibitors of CYP2C8 (e.g., gemfibrozil) and strong inducers of CYP2C8 (e.g., rifampin/rifampicin).

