# tablets per day: 1 tablet per day: 1mg, 2mg, 4mg, 6mg, 8mg, 10mg 2 tablets per day: 12mg, 16mg 3 tablets per day: 24mg																																																																																			
Duration of Exposure Record	Under Compliant	Compliant	Over Compliant																																																																																
1 – 14 days	< 1 dose	1 dose	> 1 dose																																																																																
15 – 42 days	< 1 dose	1 or 2 doses	> 2 doses																																																																																
43 – 70 days	< 2 doses	2 or 3 doses	> 3 doses																																																																																
71 – 98 days	< 3 doses	3 or 4 doses	> 4 doses																																																																																
99 – 126 days	< 4 doses	4 or 5 doses	> 5 doses																																																																																
Etc.																																																																																			
Duration of Exposure Record	Under Compliant	Compliant	Over Compliant																																																																																
1 – 7 days	< 1 dose	1 dose	> 1 dose																																																																																
8 – 21 days	< 1 dose	1 or 2 doses	> 2 doses																																																																																
22 – 35 days	< 2 doses	2 or 3 doses	> 3 doses																																																																																
36 – 49 days	< 3 doses	3 or 4 doses	> 4 doses																																																																																
50 – 63 days	< 4 doses	4 or 5 doses	> 5 doses																																																																																
64 – 77 days	< 5 doses	5 or 6 doses	> 6 doses																																																																																
78 – 91 days	< 6 doses	6 or 7 doses	> 7 doses																																																																																
92 – 105 days	< 7 doses	7 or 8 doses	> 8 doses																																																																																
Etc.																																																																																			

Exposure and Compliance			
○ Darbe Every Week Exposure Records: Based on Number of Doses Given			
Duration of Exposure Record	Under Compliant	Compliant	Over Compliant
1 – 3 days	< 1 dose	1 dose	> 1 dose

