4 – 10 days	< 1 dose	1 or 2 doses	> 2 doses
11 days	< 1 dose	1 or 2 or 3 doses	> 3 doses
12 – 17 days	< 2 doses	2 or 3 doses	> 3 doses
18 days	< 2 doses	2 or 3 or 4 doses	> 4 doses
19 – 24 days	< 3 doses	3 or 4 doses	> 4 doses
25 days	< 3 doses	3 or 4 or 5 doses	> 5 doses
26 – 31 days	< 4 doses	4 or 5 doses	> 5 doses
32 days	< 4 doses	4 or 5 or 6 doses	> 6 doses
33 – 38 days	< 5 doses	5 or 6 doses	> 6 doses
39 days	< 5 doses	5 or 6 or 7 doses	> 7 doses
40 – 45 days	< 6 doses	6 or 7 doses	> 7 doses
46 days	< 6 doses	6 or 7 or 8 doses	> 8 doses
47 – 52 days	< 7 doses	7 or 8 doses	> 8 doses
53 days	< 7 doses	7 or 8 or 9 doses	> 9 doses
Etc.			

- Compliance will be summarized for the following time periods: Day 1 - < Week 28, Week 28 - < Week 52, Week 28 - < End of Treatment, and Day 1 - < End of Treatment (Overall compliance).
- Within each period, the percentage of time that a subject spent in each of the 3 categories above or with missing compliance data will be determined and will be based on the durations of each record within the period.
- A subject's compliance category will be the category that corresponds to the highest percentage of total time. In the unlikely event of a tie, the lower compliance category will be chosen (i.e., in a tie between under and compliant, under is chosen; in a tie between compliant and over, compliant is chosen; and in a tie between under and over, under is chosen; in a tie with missing, missing is chosen).

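### Darbepoetin compliance is judged record by record with a one-dose allowance and no cumulative check, so the category depends on how exposure records are split

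*SAP*

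**What the plan says.** Section 10.6.2.5 sets the unit of assessment for both arms: "A compliance category will be assigned to each randomized treatment exposure record according to the following tables".

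- **Daprodustat.** The test is a percentage of tablets. A record is in the middle category under "Compliance for the exposure record ≥ 80% and ≤ 120" (per cent) and over compliant under "Compliance for the exposure record > 120" (per cent).
- **Darbepoetin.** The test is a count of injections that depends on record length and frequency. The 4-weekly table, headed "Darbe Every 4 Week Exposure Records: Based on Number of Doses Given", has the row "15 – 42 days < 1 dose 1 or 2 doses > 2 doses", reading from under compliant through compliant to over compliant. The 2-weekly table has "22 – 35 days < 2 doses 2 or 3 doses > 3 doses". The weekly table accepts 4 or 5 doses for 26 to 31 days.
- **From record to subject.** In either arm the subject's "category will be the category that corresponds to the highest percentage of total time" in the period. Zero-dose records assigned by the IRT count as compliant, and gaps between records count as under compliant.

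The category is used in two places. Section 6.2.6 tabulates it by arm. Section 10.1.1 lists as Per-Protocol exclusion 03: "Non-compliance with randomized treatment (compliance category of under compliant or over compliant) during the EP". That section says a subject meeting a criterion may be excluded and that exclusions go through blinded review.

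**The concern.** An allowance of one injection makes sense where a dose falls on the boundary of a record. But a boundary injection belongs to one record only, so over a run of adjoining records the allowance is needed about once. The tables grant it every time, and no later step checks the total. The same dosing history can then change category according to where the site closed one record and opened the next.

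Two uses depend on this. Criterion 03 cannot flag a darbepoetin subject who is labelled compliant, so the blinded review is not prompted by that criterion. And the section 6.2.6 tables set the arms side by side although the threshold for over-compliance differs between them.

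**Working it through.** **Inputs**

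- Compliance bands: section 10.6.2.5.
- Evaluation period: Weeks 28 to 52, so 24 x 7 = 168 days (section 10.6.1).
- Visits in that period: every 4 weeks (section 10.2.1.1).
- Darbepoetin dose steps: 7 of the 10 are 4-weekly (section 10.6.3.6).
- Record length: an assumption, taken as about 28 days. Section 10.6.3.6 asks for a record at each IRT dosing instruction, except when the subject is re-dispensed to carry on with the same treatment. Two features support roughly one record per visit. The Year 1 schedule marks an IRT transaction and dispensing at each 4-weekly visit, and the note about handing unchanged treatment back (footnote 9) is attached there only to Week 2 and unscheduled visits. Section 10.6.3.6 also takes the Week 28 assigned dose from a record that starts between the Week 28 and Week 32 visits.

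**Reproducing the tables.** Rebuilt as rules, the three darbepoetin tables match every printed row, including 1 or 2 doses for a 4-weekly record of 15-42 days.

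**Accepted range per record.** Planned = record days / interval. Ratio = accepted doses / planned.

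| Regimen | Record (days) | Planned | Accepted | Ratio |
|---|---|---|---|---|
| 4-weekly | 28 | 1 | 1-2 | 100-200% |
| 4-weekly | 42 | 1.5 | 1-2 | 67-133% |
| 4-weekly | 56 | 2 | 2-3 | 100-150% |
| 4-weekly | 84 | 3 | 3-4 | 100-133% |
| 4-weekly | 168 (pattern extended) | 6 | 6-7 | 100-117% |
| 2-weekly | 14 | 1 | 1-2 | 100-200% |
| 2-weekly | 28 | 2 | 2-3 | 100-150% |
| Weekly | 7 | 1 | 1-2 | 100-200% |
| Weekly | 28 | 4 | 4-5 | 100-125% |

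**Over Weeks 28-52, 4-weekly dosing**

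- Six 28-day records: planned 6 x 1 = 6; accepted up to 6 x 2 = 12; 12 / 6 = 200%. All six records are compliant, so the subject is compliant.
- One 168-day record: accepted 6 to 7, so 12 doses would be over compliant.

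**Daprodustat, 28-day record, one tablet a day.** 0.80 x 28 = 22.4 and 1.20 x 28 = 33.6, so 23 to 33 tablets are compliant. At subject level the largest-share rule loosens this: four records at 100% and two at 0% give 400 / 6 = 67% overall, and four at 120% with two at 200% give 880 / 6 = 147%. Both subjects are compliant. Exceeding 120% in every record is flagged.

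**Under-dosing.** An 84-day 2-weekly record has 6 planned doses. Five given is 5 / 6 = 83%, which the 78-91 day row calls under compliant. A daprodustat record at 83% is compliant.

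**The case against.** The strongest reply is that the counting tables have a purpose. Injections are whole events, most visits have a window of a week either side, and the 15-42 day row is 28 plus or minus 14 days, so a record can properly hold an injection at each end. A percentage band cannot work on a record with one planned dose. This stands as a defence of the tolerance within a record. It does not explain granting it six times in succession.

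Record length is also not fixed by the plan. Where re-dispensing leaves one record open for 42 days or more, doubled 4-weekly dosing is caught. The 200% figure therefore depends on records of about 28 days, which the schedule makes likely but does not guarantee.

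The plan separately summarises discrepancies between IRT-assigned and eCRF-recorded dosing (section 6.2.6), and gives no sign that sustained doubling occurs. That is fair, but the summary does not alter the compliance category.

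A reader might infer three stronger things that the SAP does not support.

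- *That doubled dosing passes at every darbepoetin frequency.* In 28-day records it is over compliant for 2-weekly dosing (4 doses, limit 3) and weekly dosing (8 doses, limit 5). It passes there only with records of about 14 or 7 days.
- *That daprodustat subjects outside 80-120% are removed from the Per-Protocol population.* The band applies to a record, the subject takes the category with most time, and exclusion is discretionary after blinded review.
- *That the rule selects against daprodustat.* The 83% example runs the other way.

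**Conclusion.** The defect holds in a limited form. Darbepoetin compliance has no cumulative check, and its category depends on how the exposure is divided into records. Its largest effect is on 4-weekly dosing: up to 200% of planned injections over Weeks 28-52 counts as compliant if records run about 28 days, against 117% if the same table pattern were applied to the period as one record. In 28-day records every darbepoetin frequency has an upper limit above daprodustat's 120% per record.

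The consequence is confined to the by-arm compliance tables, Per-Protocol criterion 03 and the supportive Per-Protocol Hgb analysis in section 7.1.2.5. Both co-primary analyses use the ITT population and are untouched. The SAP gives no basis for the number of subjects affected or the direction of any selection. Severity: minor.

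**What to change.** In section 10.6.2.5, compute the subject's category once per analysis period in both arms, as 100 x taken / planned.

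- **Planned:** the sum over records of days divided by the assigned interval (for daprodustat, days times tablets per day), leaving out IRT-assigned holds. Gaps between records, now classed as under compliant, should stay in the planned total with nothing taken. State how a record that straddles a period boundary is apportioned.
- **Daprodustat band:** 80-120%.
- **Darbepoetin band:** the wider of 80-120% or plus or minus one dose. With 6 planned, 80-120% is 4.8 to 7.2, so both versions accept 5 to 7. With 4 planned, 80-120% is 3.2 to 4.8 and would accept only 4; the one-dose allowance gives 3 to 5, so a single early, late or missed injection is tolerated when few doses are planned. With 1 planned, plus or minus one would admit zero, so keep the present floor that no dose given is under compliant.

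Use this category for Per-Protocol exclusion 03. The section 6.2.6 display of time spent in each category can stay per record, with a footnote that the record-level bands differ by arm.

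The cost is a small change to one derivation using data already collected, to be made before unblinding. Some subjects in either arm may change Per-Protocol status. No dose or schedule is altered.
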